4 PATIENT POPULATION

4.1 Eligibility of Patients

Up to 28 patients are expected to be enrolled. All centers have been selected on the basis of their extensive experience with treatment of patients with FAP, their participation in Study ALN-TTR02-002, and have the equipment necessary to treat patients in case of an emergency.

4.2 Inclusion Criteria

Each patient must meet all of the following criteria within the Screening/Baseline period to be enrolled in the study:

1. Patients have previously received and tolerated ALN-TTR02 in Study ALN-TTR02-002.
2. Karnofsky performance status of 60% or greater.
3. Absolute neutrophil count (ANC) ≥ 1500 cells/mm³, platelet count $\geq 100,000$ cells/mm³, and hemoglobin ≥ 10 g/dL.
4. Adequate liver function, demonstrated by an aspartate transaminase (AST) and alanine transaminase (ALT) levels $\leq 2.5 \times$ the upper limit of normal (ULN), total bilirubin level within normal limits, albumin >3 g/dL, international normalized ratio (INR) ≤ 1.2 .
5. Adequate renal function, demonstrated by serum creatinine level $\leq 1.5 \times$ ULN.
6. Women of child-bearing potential must have a negative pregnancy test, cannot be breast feeding, and must be using 2 highly effective methods of contraception prior to screening, throughout study participation, and for 75 days after the last dose of study medication. Highly effective methods of birth control are defined as: hormonal - oral, implantable, injectable, or transdermal contraceptives in conjunction with spermicide, condom, or diaphragm; mechanical - spermicide in conjunction with a barrier such as a condom or diaphragm; intrauterine device in conjunction with spermicide or condom; or surgical sterilization of partner in conjunction with spermicide, condom, or diaphragm.
7. Males agree to use appropriate contraception throughout study participation and for 75 days after the last dose of study medication.
8. Patient is willing and able to comply with protocol-required visit schedule and visit requirements and provide written informed consent.

Additional inclusion criteria for patients participating in the PK/PD subgroup include:

9. At the time of enrollment, at least 6 months have elapsed since the patient's last dose of ALN-TTR02.

Additional inclusion criteria for patients participating in the Cardiac subgroup:

10. Have a left ventricular wall thickness of ≥ 13 mm on transthoracic echocardiogram.

11. Be normotensive or have hypertension that is well-controlled.
12. Absence of aortic valve disease.

4.3 Exclusion Criteria

Patients meeting any of the following criteria within the Screening/Baseline period (Day -28 to Day 0) will be excluded from the study:

1. Patient is pregnant or nursing.
2. Patient has had a liver transplant.
3. Has a known or suspected systemic bacterial, viral, parasitic, or fungal infection.
4. Patient received an investigational agent, other than tafamidis or diflunisal, within 30 days prior to first dose study drug administration.
5. Patient has a New York Heart Association heart failure classification >2 (see Appendix 3).
6. Patient has unstable angina.
7. Patient has uncontrolled clinically significant cardiac arrhythmia.
8. Patient is considered unfit for the study by the Principal Investigator (PI).

4.4 Blinding Procedure

This is an open-label, single-arm study; all patients will receive 0.3 mg/kg ALN-TTR02. No blinding procedures will be needed.

4.5 Early Patient Withdrawal

Patients are free to withdraw from the study at any time and for any reason, without penalty to their continuing medical care. A patient will be considered to have completed the study if the patient completes protocol-specified procedures up through the 21-day Follow-up visit for patients continuing into the global extension study, and up through the 56-day Follow-up visit for Year 2 for patients not continuing into the global extension study. For patients who withdraw from the study early, every effort should be made to complete the Early Termination (ET) visit.

4.5.1 Reasons for Withdrawal

The Investigator may withdraw a patient from the study if the patient:

- Is in violation of the protocol
- Experiences a serious or intolerable adverse event (AE)
- Develops conditions listed in the exclusion criteria during the course of the study
- Becomes pregnant
- Requires a prohibited medication (see [Section 5.10](#))
- Requests to be withdrawn from the study
- Is found to be considerably non-compliant with the protocol required ALN-TTR02 dosing visits

A patient may be withdrawn from the study if, in the Investigator's opinion, they are unable to continue. The Investigator will also withdraw the patient from the study upon the request of Alnylam, including if Alnylam terminates the study. Upon occurrence of a serious or intolerable AE, the Investigator will confer with Alnylam before discontinuing the patient. A patient may withdraw consent to participate in the study at any time.

Missing an occasional dose of study medication will not necessarily result in the patient being withdrawn from the study. However, if a patient misses 3 consecutive doses of ALN-TTR02, the Investigator at the site and the Medical Monitor will determine whether the patient will be withdrawn from the study. If the patient is withdrawn from the study, the reason will be noted on the case report form (CRF).

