5.7 Criteria for Dose Modification or Discontinuation of Study Drug

If a study drug related AE occurs in a patient that the Investigator judges as presenting a potential risk to the patient for further dosing, the Medical Monitors and Investigator will review all available safety data for that patient and for all other patients enrolled in the study. Based on this review it may be decided to discontinue further administration of ALN-TTR02, or, if the Investigator concurs, the patient may resume ALN-TTR02 as before or any of the following modifications may be instituted for that patient: reduce the dose of ALN-TTR02 to 0.15 mg/kg, modify the premedication regimen, and/or increase the number of weeks between dosing.

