6 STUDY VISITS

The duration of a patient's participation in this study is approximately 2 years and 4 months.

Screening/Baseline evaluations are to be performed within 28 days before receiving the first dose of study drug, as indicated in Table 1-1 and (Appendix 2 provides the schedule of assessments for patients administered ALN-TTR02 once every 4 weeks). Patients determined to be eligible based on Screening/Baseline assessments will receive treatment (IV infusion of study drug) once every 3 or 4 weeks; based on results from the ongoing ALN-TTR02-002 study where the safety and PD of 2 dosing schedules are being evaluated. Patients will remain at the study site for at least 1 hour following completion of dosing for observation and for PK sampling. Subjects in the PK/PD subgroup will remain at the study site for 6 hours following completion of dosing following the first dose and the doses given at 8 and 24 months for additional PK sampling. Patients will return to the study site for clinical activity assessments approximately once every 6 months.

All patients who discontinue the study before the 56-day Follow-up visit (or before the 21-day Follow-up visit for those patients continuing into the global extension study) will return to the study site for their Early Termination visit assessments.

Visiting nurses may conduct interim PK/PD visits.

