6.3 Early Termination

For patients who withdraw early from the study, every effort will be made to have them return to the study site to have the following procedures performed.

- Perform a physical examination, including weight.
- Measure vital signs.
- Perform a 12-lead ECG.
- Collect blood samples for clinical laboratory tests, including:
 - Hematology
 - Serum chemistries
 - Coagulation studies
 - Thyroid function tests
- Collect blood samples for serum TTR protein and secondary PD biomarker analysis. Additionally, aliquots of serum samples will be taken and frozen, to permit testing of additional proteins related to FAP.
- Collect blood sample for PK analyses
- Collect urine sample for PK analyses
- Collect urine sample for urinalysis.
- Perform clinical activity assessments once, only in patients who withdraw >3 months after the last clinical activity assessments were performed and who received at least 4 doses of study drug.
 - mNIS + 7
 - VDT
 - Grip strength
 - Ten-meter walk test
 - mBMI
 - NIS
 - HRdb
 - COMPASS 31 survey
 - Pharmacoeconomics questionnaire
 - EQ5D
 - R-ODS
 - PND score
 - FAP stage
 - Collect paired 3-mm skin punch biopsies for IENFD analysis
- Perform an ophthalmology examination.
- For patients enrolled in the Cardiac subgroup:
 - Perform an echocardiogram

- Collect blood sample for assessment of NT-proBNP and troponin I
- Obtain concomitant medications information.
- Document any AEs.

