8.4 Adverse Event Reporting

The Investigator is responsible for reporting all AEs that are observed or reported after the first dose of study drug regardless of their relationship to study drug through the 21 or 56-day Follow-up visit (depending on whether or not the patient plans to enroll into the open-label global extension study).

Any medical condition that is present when a patient is screened and does not deteriorate should not be reported as an AE. However, if it does deteriorate at any time during the study, it should be reported as an AE.

All AEs must be fully recorded in the site's source records and in the patients' CRF, whether or not they are considered to be drug-related. Each AE should be described in

detail: onset time and date, description of event, severity, relationship to investigational product, action taken, and outcome (including time and date of resolution, if applicable).

Adverse events should be followed for the reporting periods defined earlier or until recovery to the normal state has been achieved, whichever occurs first. In the event of a patient not returning to the clinical unit, the outcome of this event will be recorded as lost at follow-up.

For patients who withdraw from the study early, ongoing AEs will be followed until resolution or 28 days from last dose, whichever occurs first.

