8.5 Adverse Event Reporting Period

As stated in [Section 8.4](#), AEs will be assessed for 21 or 56 days following the last dose of study drug (depending on whether or not the patient plans to roll over to the open-label global extension study) or until recovery to the normal state has been achieved, whichever occurs first; all AEs that occur after the start of study drug administration on Day 0 (Baseline) must be reported in detail on the appropriate CRF page and followed to satisfactory resolution, or a period of 21 or 56 days after the last dose of study drug administration (depending on whether or not the patient plans to roll over to the open-label global extension study), whichever is shorter.

Serious AEs will be followed for 21 or 56 days following the last dose of study drug (depending on whether or not the patient plans to roll over to the open-label global extension study), or until satisfactory resolution, or until the SAE is considered by the Investigator to be chronic or the patient is stable, whichever occurs first.

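### Protocol 8.4 ends follow-up of an early leaver's ongoing adverse events at 28 days from last dose, where 8.5 gives 56 days to a patient not rolling over

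*Protocol*

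**What the plan says.** **Leaving the study.** Protocol 4.5.1 lists reasons for which the investigator may withdraw a patient. They include a serious or intolerable AE and "Develops conditions listed in the exclusion criteria during the course of the study". The exclusion criteria in 4.3 range from "Patient has a New York Heart Association heart failure classification >2" to "Has a known or suspected systemic bacterial, viral, parasitic, or fungal infection".

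**Stopping drug.** Protocol 5.7 covers a drug-related AE judged to make further dosing risky: "Based on this review it may be decided to discontinue further administration of ALN-TTR02". The alternatives are to resume as before, reduce the dose, change the premedication or lengthen the dosing interval.

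**AE follow-up.** The first paragraph of 8.4 has AEs reported through the 21-day or 56-day visit, depending on planned rollover. Its last paragraph sets a separate rule: "For patients who withdraw from the study early, ongoing AEs will be followed until resolution or 28 days from last dose", whichever comes first. Section 8.5 says "AEs will be assessed for 21 or 56 days following the last dose of study drug", again by rollover status, or until recovery if that is sooner. It does not mention early withdrawal. Section 8.11 follows all serious AEs (SAEs) until resolved, chronic or stable.

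**Visits.** Section 6 sends "All patients who discontinue the study before the 56-day Follow-up visit" (21-day for rollover patients) to an Early Termination (ET) visit, whose content is in 6.3. Section 6.2.5 times the two follow-up visits from last dose and requires both of anyone not entering the extension study. Section 6.2.5.2 lists only blood sampling for the 56-day visit, whereas Table 1-2 footnote x runs AE documentation through it.

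**Analysis.** SAP 4.6.2 counts an AE as treatment-emergent if it starts within 28 days after last dose, and lists all on-study AEs.

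**The concern.** Long-term safety is the primary objective (Protocol 2.1). A patient who stops because of an intolerable AE is one whose outcome the study most needs to record, yet this is the group to which 8.4 applies the shorter limit. An AE still present on day 28 could be left as ongoing in the database, while the same AE in a non-rollover completer would be followed for up to another 28 days.

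Sites also have two instructions for one patient. One site may close follow-up at day 28 under the last paragraph of 8.4, and another may continue to day 56 under 8.5. AE outcomes and durations for early leavers would then depend partly on which paragraph the site applied.

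**Working it through.** There is no sample-size, power or error-rate figure to reproduce: SAP 3.1 says the sample size was not based on power. The check compares the stated limits.

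**1. Longest follow-up of an ongoing non-serious AE, counted from last dose**

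| Patient | Limit | Source |
|---|---|---|
| Rolls over | 21 days | 8.5 |
| Completes, does not roll over | 56 days | 8.5; 8.4 first paragraph (through the 56-day visit) |
| Withdraws early | 28 days | 8.4 last paragraph |
| Withdraws early, does not roll over, read under 8.5 | 56 days | 8.5, which has no exception |

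**2. Differences**
- Early leaver against non-rollover completer: 56 − 28 = 28 days shorter, and 28/56 = 50%.
- Early leaver against rollover patient: 28 − 21 = 7 days longer.

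**3. Does 28 days match a follow-up visit?** In the 3-weekly schedule the last dose is on Day 735 (Table 1-2). Follow-up visits are at 735 + 21 = Day 756 and 735 + 56 = Day 791. Twenty-eight days after last dose would be 735 + 28 = Day 763, when no visit is scheduled. The 56-day limit has a visit attached; the 28-day limit does not.

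**4. Which AEs are affected?** The last paragraph of 8.4 refers to ongoing AEs without setting SAEs apart. Section 8.11 gives SAEs no day limit; 8.5 does cap them, at 21 or 56 days. Taking 8.11, the dedicated SAE section, as governing, the 28-day limit bears mainly on non-serious AEs. Those include intolerable AEs that ended treatment without meeting a seriousness criterion.

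**5. Does an early leaver attend the 56-day visit?**
- For: 6.2.5 requires both follow-up visits of patients not entering the extension study and counts from last dose, so its words can cover an early leaver. Section 4.5.2 also keeps patients withdrawn for medical reasons under safety follow-up.
- Against: Section 6 and 6.3 name only the ET visit for early leavers, and 4.5.2 does not say which procedures or for how long.
- Result: attendance is ambiguous. So is access to the 4-weekly transthyretin (TTR) recovery checks, which follow the 56-day visit (6.2.5.2, 6.4).

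**6. Does SAP 4.6.2 settle the 28 days?** No. Its window concerns when an AE starts, for tabulation. The rule in 8.4 concerns how long an AE already present is followed.

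**The case against.** **A specific rule governs a general one.** The 28-day sentence is written for early leavers, and 8.5 opens by referring back to 8.4, so the two can be read together with 28 days as a deliberate limit. That reading is fair, and it reduces the conflict to a missing cross-reference. It leaves the substance in place: a shorter limit for patients who may have left because of an AE.

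**Twenty-eight days is not the shortest limit.** Rollover patients have 21. This is correct, and halving relative to 56 days should not be quoted without it. Rollover patients move into another study, whose AE collection these documents do not describe.

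**Withdrawal is discretionary.** A reader might infer that a passing infection forces a patient out, or that stopping drug means leaving the study. The documents do not support either. Section 4.5.1 says the investigator may withdraw. Occasional missed doses do not necessarily lead to withdrawal, and three in a row prompt a case review. Section 5.7 is worded about drug only and offers several steps short of stopping. It names no later visits, but that silence does not end participation.

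**Early leavers do have a route to day 56.** A reader might infer that they have none. Section 6.2.5 gives a plausible one, so the defect is ambiguity, not absence.

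**TTR recovery.** A reader might argue from Protocol 1.3 (recovery beginning around Day 21-28, baseline by Day 70) that follow-up stops while the drug is still acting. Those data are single-dose, in healthy volunteers, and nothing in the documents ties resolution of an AE to TTR level. The point does not rest on them.

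**Conclusion.** The point holds in a narrow form and is minor. For an early leaver who does not roll over, 8.4 caps follow-up of ongoing AEs at 28 days, against 56 days in 8.5 and the opening of 8.4. Attendance at the 56-day visit is not clearly stated. This rests on two assumptions: that 8.11 governs SAEs, and that 8.5, having no exception, also covers early leavers.

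The effect on results is not estimable, because the documents give neither a withdrawal rate nor leavers' outcomes. It may be small: the parent study reported no discontinuations, with two doses per patient (Protocol 1.3), and no subject in the earlier lipid-nanoparticle studies stopped for an infusion-related reaction (1.6.2.1).

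A reader might go further and infer that selective loss biases the later by-visit clinical activity summaries, so that off-drug 6-monthly visits or moving ET results into scheduled months are needed. The documents do not establish that. The study is single-arm and descriptive, and SAP 3.10 already tabulates by recorded visit. Scheduled mNIS+7 values average two assessments (SAP 7.1) while the ET assessment is done once (Protocol 6.3). Those are trade-offs, not errors.

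**What to change.** 1. **Protocol 8.4:** replace 28 days with 56 days from last dose for early leavers who do not roll over.
2. **Protocol 6.3:** state that early leavers who consent also attend the existing 56-day visit under 6.2.5, and the 4-weekly TTR checks where they apply. Those who decline have an AE check by telephone.
3. **Protocol 6.2.5.2:** add AE documentation to the listed procedures, to match Table 1-2 footnote x.
4. **SAP 4.6.2:** keep the 28-day treatment-emergent tables, and show AEs with onset on days 29 to 56 after last dose separately.

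The cost is wording in three protocol sections, a sentence in the SAP, and one already scheduled visit or one call per early leaver, plus the TTR checks where they apply. The downside is the burden on patients who may be unwell, which is why the visit depends on consent and has a telephone alternative.

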4.5.2 Handling of Withdrawals

In the event a patient is withdrawn from the study, the contract research organization (CRO) Medical Monitor must be informed immediately. If there is a medical reason for withdrawal, the patient will remain under the supervision of the Investigator for protocol-specified safety follow-up procedures.

Patients who voluntarily withdraw are termed dropouts. Dropouts will not be replaced.

If a patient is withdrawn/withdraws every effort should be made to conduct the ET visit. Patients who fail to return for final evaluations will be contacted by the site in an attempt to have them comply with the protocol. The site will follow-up by telephone at least twice and send a registered letter to any patient who fails to return for the final evaluation.

When a patient withdraws from the study, the primary reason for discontinuation must be recorded in the appropriate section of the CRF and all efforts will be made to complete and report the observations as thoroughly as possible.

5 STUDY MEDICATION

5.1 Presentation of Study Drug

ALN-TTR02 Solution for Injection is an RNAi therapeutic consisting of an siRNA targeting TTR mRNA formulated in LNPs. The ALN-TTR02 drug product is a sterile formulation of TTR siRNA with lipid excipients (DLin-MC3-DMA, DSPC, cholesterol, and PEG₂₀₀₀-C-DMG) in isotonic phosphate buffered saline. ALN-TTR02 Solution for Injection contains 2 mg/mL of TTR siRNA drug substance.

The ALN-TTR02 drug product is packaged in 10 mL glass vials with a fill volume of 5.5 mL. The container closure system consists of a United States Pharmacopeia/European Pharmacopoeia (USP/EP) Type I borosilicate glass vial, a Teflon-faced butyl rubber stopper, and an aluminium flip-off cap.

5.2 Preparation of Study Drug

Each investigational site will be responsible for IV preparation and labeling according to separate handling instructions and allocating treatments to the patients.

The pharmacist will prepare the study drug under aseptic conditions. The amount (in mg) of ALN-TTR02 to be administered will be determined based on the patient's weight (kg). For each dose administered, the weight obtained during the previous dosing day should be used to calculate the dose of study drug. In the event that the weight obtained on the previous dosing day is not available, the weight obtained pre-dose on the dosing day can be used for dose calculation. Patients who weigh 105 kg or more will receive ALN-TTR02 dosing based on an assumption of a body weight of 104 kg.

A total of 200 mL will be infused into patients. Sterile normal saline (0.9% NaCl) will be added to a sterile infusion bag, and the calculated volume of ALN-TTR02 will be withdrawn from the vials and injected into the infusion bag.

Additional study drug preparation details are provided in the ALN-TTR02 Pharmacy Manual.

5.3 Storage of Study Drug

All study drug must be stored in a secure, temperature controlled location and may be dispensed only by a staff member specifically authorized by the Investigator or by a pharmacist, as appropriate. All study medication will be stored upright and refrigerated at approximately 5 ± 3°C. Any deviation from the recommended storage conditions should be reported to the CRO and/or Alnylam and use of the study drug halted until authorization for its continued use has been given by Alnylam or designee.

No special procedures for the safe handling of ALN-TTR02 are required. Alnylam will be permitted, upon request, to audit the supplies, storage, dispensing procedures, and records.

No trial product(s) may be administered to any person not enrolled in the trial.

Additional storage details are provided in the ALN-TTR02 Pharmacy Manual.

5.4 Labeling and Packaging of Study Drug

All packaging and labeling as well as the preparation of ALN-TTR02 IV will be in compliance with Good Manufacturing Practice (GMP) specifications, as described in the

Manufacture of Investigational Medicinal Products Volume 4 Annex 13, and any other or local applicable regulations.

Study drug labels will include all appropriate local labeling requirements on the vial and external label. Sample labels will be submitted to health authorities, per local country submission requirements.

